5 GENERAL ISSUES FOR STATISTICAL ANALYSIS

All analyses will be conducted two-sided and significance interpreted at the 5% level.

5.1 Blinding of the statistical analysis

The study statistician (SB) was not blinded in this study because of (a) the allocation ratio making obvious which group was which and (b) SB handling data to produce the DMC reports.

5.2 Analysis populations

We are conducting three distinct types of statistical analyses within this trial: **cross-sectional** analyses, **cohort** analyses and analyses on **safety** outcomes. Here we define the populations pertaining to each. We define an Intention to Treat Population (ITT) although no strict ITT analysis is planned as part of the main analysis of this trial. We do not describe a per protocol population — no per protocol analyses are planned.

5.2.1 Intent-to-treat analysis population

For each effectiveness outcome, populations for the cross-sectional and cohort analyses are defined as follows:

(a) Cross-sectional analyses –

A strict intention to treat population is difficult to define in a cluster randomised trial, as our intention was to treat all those resident in the home, but we can only include those who agree to participate. For the cross-sectional analysis, outcome data have been collected on the majority of residents in the homes at 12 months. Those residents who had entered a home after a pre-specified cut-off date i.e. after 9 months post-randomisation, have been excluded on the grounds that they would not have experienced a sufficient dose of the intervention. This cut-off date was around three months prior to the final outcome data collection in most homes but between two and three months prior to outcome data collection in seven homes in which final outcome data collection occurred during the 12th month rather than at the end of the 12th month. The intention-to-treat population comprises all those resident in the home who consented to intervention (or data collection) at or prior to the cut-off assessment date at their home. Residents that moved will be considered in the home that they have moved to providing that they have been resident there prior to the cut-off date. If they were not resident in the home prior to the cut-off date they will be analysed as if they were still resident in the home in which they originally gave consent.

(b) Cohort analyses -

The intention to treat population is those who provided data at baseline. For those residents that move, they will be assigned to the home in which they started out. For most outcomes the ITT population is all participants who provided the outcome measure of interest prior to randomisation but for the outcome 'remission of depression' it is residents depressed at baseline.

Barts and The London School of Medicine and Dentistry

Pragmatic Clinical Trials Unit

5.2.2 Available-case analysis population

By the nature of the participants included in the study, many will not be able to provide complete data at each time point. For each outcome the available case population will be defined by the number of people able to provide data for that outcome, thus the population will be different for each outcome.

(a) Cross sectional analyses-

Therefore, for this type of outcome, we use intention to treat principles, and include all those residents in the home who consented to intervention (or data collection) at or prior to the 9 month assessment date at their respective home and who have a valid outcome measure at the end of the study (12 months) (i.e. complete case following the ITT principle). Residents who switch homes will be included in the analysis with the home in which they move to if they have been resident in this home prior to the 9 month cut off. Otherwise they will be analysed as if they were still in the home in which they were originally randomised as long as there is an outcome measure collected within 2 months either side of the point 12 months from randomisation

(b) For cohort analyses-

We will include all those who gave consent/assent, with a valid baseline measure of outcome before randomisation, resident in a participating home and with a valid outcome measure at the relevant time point (either 6m or 12m). Residents who move to another trial home and are therefore still followed up will be analysed according to their original allocation (i.e. either intervention or control, ITT principle) in the home as if they were in the home in which they first resided. For remission of depression this includes only those who had symptoms of depression at baseline.

5.2.3 Per protocol analysis population

We have not defined a per protocol population; it is unclear what such a population would be.

5.2.4 Safety population

For the safety analyses the population is defined as all those in the home at any time during the intervention period with exposure given by the length of time within the home during the intervention period i.e. person months of exposure, which will form the denominator

The safety outcomes are deaths and peripheral fractures, both classified as serious adverse events (SAEs). For deaths the study population is all residents present in the home during the intervention period.

Data on peripheral fractures will be collected in two ways and different populations are defined for each

- a. Events in study participants (data available at the level of the individual)
- b. Events in all residents (data available aggregated at the level of home).

For deaths and for peripheral fractures where the event is measured on all participants the denominator is person years of exposure. This allows us to include residents who were neither present at the beginning nor the end of the study.

Barts and The London School of Medicine and Dentistry

Pragmatic Clinical Trials Unit

5.2.5 Other populations

Unconventional movements of some residents through the trial need to be accommodated in the analysis.

- (i) All residents in one home got moved temporarily to another home in the opposite trial arm and were moved back to their original home before the end of follow-up. They will be analysed in the home where they resided at the outset.
- (ii) Residents who move to another study home part way through will have two follow-up reference points. E.g. study participant X had been living in home A since pre-randomisation. In month 8, X moves to home B (which may or may not be in the same trial arm as home A) which had been randomised only 5 months previously. Therefore, when home B is due for its 6-month assessment visits, resident X will be due a 9 month assessment. Follow-up (12 months) would be due to end for participant X at the 9 month assessment of home B. However, for the cross-sectional analysis, assuming resident X is still present, they may have additional follow-ups and their latest follow-up will be the one that is included in the 12 month assessment of home B. Resident X, in the cohort analysis, would be analysed as belonging to home A, not B. In the cross-sectional analysis, X is treated as residing in B unless they have been in B for a relatively short time (see sections 5.2.2 and 5.2.3).

5.3 Database

5.3.1 Description

Questionnaires were completed on paper with the resident. Data were entered directly onto a study laptop after the assessment time with the resident by the recruitment team.

The database is stored in Microsoft Access 2007 as a series of separate tables.

5.3.2 Data quality

Quality assurance checks will be undertaken by Warwick CTU to ensure the integrity of randomisation, data entry procedures and data collection.

A 10% random sample will be checked against paper records to identify data entry errors. At the level of the home, the records of 8 homes will be checked. Should the error rate exceed 0.1% of all data items recorded, a further sample of 8 homes will be checked. At the level of the resident, a 10% random sample of residents' records will be selected across all homes. Data entered on the GDS-15 will be checked at item level. Should the error rate exceed 0.1%, a further 10% sample will be drawn for checking. For the other outcome measures and covariates, we will also tolerate an error rate of 0.1%.

We will fit linear regression models of the primary outcome measure (GDS-15) and main secondary outcome measure, MMSE, to see if there is any association with data input clerk (coded using dummy variables). This could reveal to us if any clerks have a tendency to input consistently high or low values for these outcomes or if there is a preponderance of missing values or zeros.

5.3.3 Database freeze

The statistician responsible for the analysis will conduct or oversee additional data checks. These include range checks, logical and consistency checks which may not be

picked up by checks performed at the individual patient level by the research staff that collect and enter the data.

Once all 12 month follow-up data have been checked and errors corrected, the database will be frozen in compliance with PCTU SOP 09c (data freeze, handover and lock).

5.4 Analysis software

The analysis will be carried out using mainly Stata version 10.1 or 11 (StataCorp. 2009). However, some analyses may be carried out using MLwiN, a specialist programme for handling multilevel data.

5.5 Methods for withdrawals, loss to follow-up and missing data

Numbers lost to follow up and withdrawal from the study will be described by arm to try and establish if there is difference in attrition rates.

Cross-sectional: N/A

Cohort analyses: as all cohort analyses will be modelled using maximum likelihood methods, outcomes will not be imputed as we do not, at this stage, wish to assume that measurements are missing at random (MAR).

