3 STUDY METHODS

3.1 Overall study design and plan

Target for randomisation: 77 RNHs (78 actual)
Date of first randomisation: 19th February 2009
Date of last randomisation: 30th April 2010

Trial design: cluster randomised, parallel group

Blinding: Clinical researchers were blinded to allocation to interpret records on

deaths.

Randomised Interventions: exercise programme + depression awareness programme vs. control

intervention (Depression awareness programme)

Planned allocation ratio: 2 intervention homes: 3 control homes

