5.7 Method for handling randomisation stratification or minimisation factors

All analyses will include the minimisation factors and the location stratification variable (i.e. centre (see 5.6)), which are categorical and defined at cluster level. Dementia specialist care home status (Yes/No) will not be included as there was, by design, only one such home.

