8.3 Primary analysis

To assess the difference in proportions depressed at 12 months between intervention and control homes we will use mixed effects modelling (with a random effect to account for clustering by RNH) with a binomial family and a logit link function (to handle the binary outcome) in Stata (xtmelogit command).

To assess the change in severity of depressive symptoms at 6 and 12 months between intervention and control homes we will use mixed effects modelling (with a random effect to account for clustering by RNH) with a Gaussian family and the identity link function in Stata (xtmixed command).

Each model will include the baseline measure of the outcome (except for MMSE), as well as the minimisation variables home type, home size and the stratification variable location. In addition, we will include individual baseline SPPB score and whether or not the resident was on antidepressants (cohort analyses only). We will also include, at the home level, the proportion of residents with moderate to severe cognitive impairment at baseline (i.e. with an MMSE<20).

We will examine the correlations between the covariates to assess any potential multicollinearity problem. This will be done by fitting a linear regression model and requesting the variance inflation factors (VIFs). A VIF>10 indicates severe multicollinearity. VIFs between 5 and 10 indicate some problem.

For the outcomes which indicate a change in severity of depression for those depressed at baseline, we will use a similar strategy, but measurements at baseline and outcome will be on the same individual. We will therefore introduce baseline levels of depression severity as a covariate at the individual level.

All covariates listed in section 5.9 will be entered into the model at the same time and none will be removed unless there is evidence of multicollinearity, in which case, the collinear covariate providing the best fit will be retained.

The regression coefficient for continuous outcomes, odds ratio for binary outcomes, proportional odds ratio for ordered outcomes and incidence rate ratio for rate outcomes, of the treatment (intervention vs. control) variable, and its 95% confidence interval, will be reported along with the p-value.

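### The SAP does not fix the estimator or reference distribution for the mixed models; read as full maximum likelihood with a normal reference, the continuous co-primaries would be tested at about 6% to 7% instead of 5%.

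*SAP*

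**What the plan says.** - **Level.** Section 5: "All analyses will be conducted two-sided and significance interpreted at the 5% level". Section 8.3 promises a 95% confidence interval and p-value for the treatment term in each model.
- **Estimator.** The only statement is in section 5.5, in a sentence explaining why outcomes are not imputed: "all cohort analyses will be modelled using maximum likelihood methods". It is limited to the cohort analyses; the cross-sectional entry there is marked not applicable.
- **Models.** Section 8.3 fits the two continuous co-primaries by a mixed model "with a Gaussian family and the identity link function in Stata (xtmixed command", and the binary one "with a binomial family and a logit link function (to handle the binary outcome) in Stata (xtmelogit command". Each has a random effect for home. Section 5.4 allows Stata 10.1 or 11, with MLwiN for some analyses. No estimation option, reference distribution or degrees of freedom is given.
- **Clusters.** Section 3.1: "Target for randomisation: 77 RNHs (78 actual") and "Planned allocation ratio: 2 intervention homes: 3 control homes".
- **Adjustment.** Section 5.7: "All analyses will include the minimisation factors and the location stratification variable". Section 5.9 adds the home's proportion with MMSE<20 and, in the cross-sectional model, the home's baseline level of the outcome. Section 8.3: "All covariates listed in section 5.9 will be entered into the model at the same time". Section 12 reduces home type from four categories to three.

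**The concern.** The treatment effect is a between-home contrast, so its standard error depends on a between-home variance estimated from 78 units. Full ML estimates that variance without allowing for the home-level coefficients fitted alongside it, so the variance is biased downwards. A normal reference then also ignores the uncertainty in the estimate. Both errors make intervals too narrow and p-values too small. REML with a t reference based on homes avoids both.

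The choice is open, and it affects the error rate. Section 5.10 plans no multiplicity control that might absorb the excess. Section 5.1 says the study statistician is not blinded, so an estimator left open could decide a borderline result after the data are seen.

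**Working it through.** **1. Inputs from the SAP.** K = 78 homes at 2:3 (78 × 0.4 = 31.2, so 31 v 47); two-sided 5%; ICC 0.053 and mean cluster sizes at follow-up of 3.9, 7.5 and 9.6 (Table 4).

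**2. Reproducing Table 4.** With (1.960 + 0.842)² = 7.849 and total N = 7.849 × (SD/1.2)² / (0.4 × 0.6):
- C: SD 2.21 gives 110.9, or 45 + 67 = 112 in whole residents (stated 112).
- D: SD 3.12 gives 221.1, or 89 + 133 = 222 (stated 224).
- A: 46.1% v 28.8% with continuity correction gives 112 + 168 = 280 (stated 281).
- Design effects 1 + (m − 1) × 0.053: 1.456, 1.345 and 1.154 (stated 1.46, 1.34, 1.16).

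The SAP's figures reproduce, so the inputs are read correctly.

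**3. Home-level coefficients.**
- Cohort models: intercept 1, arm 1, location 1, size 1, home type 2, proportion MMSE<20 1. Total p = 7, of which five are adjusters.
- Cross-sectional model: the same plus the home's baseline outcome. Total p = 8, of which six are adjusters.

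**4. Closed form, full ML with a normal reference** (balanced homes, variance estimate not truncated at zero). The ML standard error is √((K − p)/K) times its unbiased value, so the true size is P(|t on K − p df| > 1.960 × √((K − p)/K)).
- p = 7: √(71/78) = 0.954; critical value 1.870; size 6.56%.
- p = 8: √(70/78) = 0.947; critical value 1.857; size 6.76%.

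**5. Simulation of the linear model under no effect** (ICC 0.053, p = 7, 40,000 trials per scenario). Home-size variation is assumed, because the SAP gives none.

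| Home sizes | Full ML, normal reference |
|---|---|
| Equal | 6.0% to 6.4% |
| Poisson | 6.6% to 6.7% |
| More uneven | 6.5% to 7.1% |

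The ML standard error was about 4% to 6% too small. Separately written code (20,000 trials, cluster-size CV 0.4) gave 6.6% at 7.5 per home and 6.4% at 3.9.

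Alternatives at ICC 0.053, over all scenarios run (7 to 9 home-level coefficients):
- REML, normal reference: 5.1% to 5.6%.
- Full ML, t reference: 5.6% to 7.0%.
- REML, t on homes minus home-level coefficients: 4.7% to 5.2%.

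Changing the reference alone is therefore not enough if full ML is used.

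**6. Sensitivity to ICC** (full ML, normal reference, p = 7): 5.0% to 5.3% at ICC 0; 6.1% to 6.3% at 0.02; 6.7% to 7.2% at 0.10 to 0.20.

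**7. Mixed logistic co-primary** (ML by quadrature, 46.1% depressed, p = 8, home variance on the logit scale assumed to be 0.2):
- 7.5 per home: 6.3% with a normal reference, 6.0% with t on 70 df (3,905 trials).
- 9.6 per home: 6.7% and 6.2% (3,252 trials).

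Monte Carlo standard error is about 0.4 points. A further 8,000 trials with variance 0.184 gave 6.3% and 6.0%.

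**8. Interval width.** The 97.5% point of t on 71 df is 1.994, and 1.994/1.960 = 1.017. If REML is already used, intervals widen by about 2%. From full ML with a normal reference, 1.017/0.954 = 1.066, about 7%: roughly 5% from the estimator (1/0.954 = 1.048) and 2% from the reference.

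**The case against.** The strongest reply is that the sentence in 5.5 is about missing data and does not specify an estimator. The term it uses can loosely include REML, and 8.3 names the command without an option. On that reading the linear models, even with a normal reference, run at 5.1% to 5.6%, which few would act on. This stands: a reader might infer that the SAP commits the co-primaries to tests at 6% to 7%, but the documents fix neither full ML nor the normal reference.

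Three further limits also stand.
- The 5.5 sentence covers cohort analyses only, so it is not evidence about the binary co-primary. The figures for that outcome rest on the model named in 8.3.
- A reader might count six or more home-level adjusters in every co-primary model. After section 12 collapses home type, the cohort models have five besides arm; only the cross-sectional model has six.
- The ICC of 0.053 comes from baseline GDS-15 (section 7.6). The models adjust for baseline GDS-15 and home characteristics, so the residual ICC may differ, and the excess nearly vanishes close to ICC 0.

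The reply does not remove the gap. No section names REML, a t reference or degrees of freedom, and the plain reading of the only wording available does not hold the 5% level set in section 5.

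**Conclusion.** The point holds as an under-specified analysis whose plain reading is mildly anti-conservative. If full ML with a normal reference is meant, the two continuous co-primaries run at about 6% to 7% at ICC 0.053, depending on home-size variation, with a range from about 5% at ICC 0 to about 7% at ICC 0.10 to 0.20. If REML is meant, the excess is about half a point at most. The binary co-primary runs at about 6.3% to 6.7% with a normal reference.

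These figures assume 31 v 47 homes, home-size variation chosen by the analyst, covariates unrelated to outcome and, for the logistic model, a logit-scale home variance of about 0.2. They do not show that the trial's standard errors are in fact too small. The excess is modest, but the correction is almost free and should be made before analysis.

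**What to change.** - **Section 8.3, linear mixed models.** State that they are fitted by REML, with p-values and confidence intervals from t on homes minus home-level coefficients: 78 − 7 = 71 df for the continuous co-primaries. Apply the same rule to the continuous secondary outcomes, with each model's own count.
- **Section 5.5.** Align the wording so that it names the same estimator.
- **Section 8.3, mixed logistic co-primary.** Use t on 78 − 8 = 70 df and describe it as a partial correction. If a home-level permutation p-value is added as a check, it should follow the allocation in section 3.3: stratified by centre, with minimisation on size and type and a 70% random element.

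The cost is a few sentences and one command option. For the linear models, intervals widen by about 2% if REML was already meant and by about 7% if full ML was. For the logistic model the t reference widens them by about 2% (1.994/1.960).

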5.6 Method for handling centre effects

The two recruiting centres (London and Warwickshire) will be distinguished in the analysis by a dummy variable.

5.7 Method for handling randomisation stratification or minimisation factors

All analyses will include the minimisation factors and the location stratification variable (i.e. centre (see 5.6)), which are categorical and defined at cluster level. Dementia specialist care home status (Yes/No) will not be included as there was, by design, only one such home.

5.8 Method for handling clustering effects

We will use mixed effects models with a random effect for RNH.

It is possible that there may be additional clustering effects in intervention homes only, because the exercise classes are group activities and there may be therapist effects. However, exactly who delivered each class in not recorded, though each home's activities are overseen by a primary therapist who has the most influence on how the classes are run. It is not possible to disentangle these effects, if they exist, as physiotherapists on annual or sick leave were replaced temporarily by other physiotherapists.

Therefore, we will simply quantify and describe the clustering for each outcome overall by study arm and present 95% confidence intervals for these to check if there is substantially greater clustering in the intervention arm than in the control arm.

5.10 Multiple comparisons and multiplicity

None

5.11 Method for handling non-adherence

There is no minimum attendance requirement at exercise classes. The reasons for absences have been documented. Homes are included in the analysis in the arm they were allocated to, regardless of adherence.

5.12 Method for handling time-varying interventions

Not applicable.

5.13 Method for handling outliers

Continuous data will be plotted prior to any modelling to assess potential data errors. These will be followed up with WCTU staff. After the model is fitted, appropriate regression diagnostics will be assessed.

5.14 Derived and computed variables

The primary outcome measure GDS-15 will define the variable 'depressed' if GDS15≥ 5. For those who answer less than 13 items but at least 10, we apply the following rules: depressed=Yes if GDS≥ 4 if they answered at least 11 or 12 questions.

depressed=Yes if GDS≥3 if they answered 10 items

Each item is a depressive symptom (either present (scores 1) or absent (scores 0).

If the number of items completed, n is such that: 9<n<15, the total score is to be rescaled i.e. GDS' = 15*GDS/n

MMSE (moderate-severe impairment) is defined by a total score of <20/30. If fewer than 15 items have been completed, a total score will not be computed. If between 16 and 29 items have been completed, MMSE' = 30*MMSE/n for n: 15<n<30.

Social engagement scale: if fewer than 4 items have been completed, a total score is not computed. If 4 or 5 items have been completed, SES'=6*SES/n for n = 4 or 5.

Pain now. There should only be a response to this question if the participant scored 2 or 3 on the EQ-5D pain question, otherwise set to missing. If the participant has a score of 1 on the EQ-5D pain item but 'pain now' is missing, set to 'pain now' to 0 (No).

